1.5 Correlative Studies

1.5.1. For patients treated with VMAT, we will perform an analysis of CBCT imaging during treatment, to determine the optimal patient-specific PTV margin.

2.0 STUDY OBJECTIVES

2.1 Primary Objectives

2.1.1 To determine the risk of local failure following SBRT treatment of early glottic larynx cancers.

2.2 Secondary Objectives

2.2.1 To determine patient-reported outcomes (PRO) following treatment with SBRT.

- 2.2.2 To describe the rates of grade 3-5 acute and late toxicities following treatment with SBRT.
- 2.2.3 To characterize patient utilities using EQ5D following treatment with SABR.
- 2.2.4 To determine the patterns-of-failure following SBRT. Specifically, 2-year cumulative risk of in-field, marginal, and out-of-field local failure, regional and distant failure, laryngectomy-free survival, disease-specific survival and overall survival following treatment with SBRT.

2.3 Exploratory Objectives

- 2.3.1. Identify a method to optimize PTV margins for patients treated with VMAT.
- 2.3.2. Identify tissue and circulating predictors of locoregional failure.

2.4 Endpoints

- 2.4.1 Primary endpoint: 2-year risk of local failure (i.e. anywhere in the larynx) following SBRT treatment of early glottic larynx cancer
- 2.4.2 Secondary endpoints:
 - 2.4.2.1 Patient-reported outcomes: Difference in PRO voice quality measures between baseline and 1, 3, 6, 12, 18 and 24 months following treatment:

2.4.2.1.1VHI voice-quality score2.4.2.1.2MDADI

- 2.4.2.2 Rate of grade 3-5 acute (start of treatment through 90 days from the completion of treatment) and late (after 90 days from the completion of treatment) adverse events, according to NCI's CTCAE v4.0 toxicity criteria.
- 2.4.2.3 Average patient utilities (derived from EQ-5D) at baseline, 6, 12 and 24 months from the end of treatment
- 2.4.2.5 Cumulative risk of marginal and out-of field local failure at 2 years from the start of treatment with death and prior in-field local failure as a competing risk
- 2.4.2.6 Cumulative incidence of regional failure and distant metastasis at 2 years, with death and prior locoregional failure as competing risks
- 2.4.2.7 Laryngectomy-free survival probability at 2 years
- 2.4.2.8 Overall survival at 2 years

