A third option for treating a focal larynx cancer is with the use of volumetric modulated arc therapy (VMAT), which is essentially an IMRT treatment delivered from nearly 360 degrees around the patient. This allows for many more beam angles than static field IMRT and it also allows for a much quicker treatment. One group recently compared 2-arc VMAT with a typical 8-field IMRT plan for early stage larynx cancer and reported that both target volume coverage and homogeneity were comparable between VMAT and IMRT, while VMAT was superior for carotid-artery sparing. Additionally, VMAT delivery time was significantly faster than with IMRT (3-5 minutes vs. 5-10 minutes).[29] Another study supports the substantially reduced treatment time with arc therapy vs. IMRT.[30] Because of the promising results with VMAT treatment delivery, either modality (i.e. CyberKnife or VMAT) is acceptable for treatment on this protocol.

Summary points

- 1. Local control rates using a highly focal radiation target appear to be as good as conventional radiation therapy (≥80%)
- 2. Highly focal radiation therapy targeting only the involved site of disease plus a small margin delivers an extremely low dose of radiation dose nearby structures based on both the Dutch Erasmus and the UT Southwestern Phase I studies.
- 3. A reduced dose to nearby structures might improve toxicities, such as esophagitis and stroke from carotid atherosclerosis and could reduce the decline in voice function from contralateral cord dose. However, long-term follow-up of voice quality of life following focal larynx radiation therapy is not yet available from the phase I portion of this trial.
- 4. Hypofractionated radiation therapy appears to be safe, although there were three cases of soft tissue necrosis in the phase I trial. Current smoking status and larger PTV volume (> 10cc) all had qualitatively higher rates of necrosis.
- 5. Based on the phase I study, we propose using a dose of 42.5 Gy in 5 fractions for low-risk tumors: tumors with a PTV < 10cc, no recent smoking, and disease limited to the vocal process. This provides both an adequate tumoricidal dose, and a limited dose to normal tissues. Remaining patients will be irradiated using the Dutch 16 fraction regimen.
- 6. Treatment with either Cyberknife or VMAT will be acceptable.

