7.2.1 Definition

An adverse event is defined as any untoward or unfavorable medical occurrence in a human research study participant, including any abnormal sign (for example, abnormal physical exam or laboratory finding), symptom, clinical event, or disease, temporally associated with the subject's participation in the research, whether or not it is considered related to the subject's participation in the research.

Adverse events encompass clinical, physical and psychological harms. Adverse events occur most commonly in the context of biomedical research, although on occasion, they can occur in the context of social and behavioral research. Adverse events may be expected or unexpected.

Acute Adverse Events

Adverse events occurring in the time period from the start of treatment, through 90 days post treatment will be considered acute adverse events.

Late Adverse Events

Adverse effects occurring in the time period from the end of acute monitoring, to 36 months post treatment, will be defined as late adverse events. These events will include all adverse events reported directly to a member of the study team and will be captured, assessed, graded and reported as appropriate.

In addition, the study team will review encounters in the following select specialty categories relevant to study endpoints: radiation oncology, medical oncology, and otolaryngology. The queried encounters will be limited in scope based on categorization of events; namely, encounters that related to any head and neck or gastrointestinal event or problem.

Severity

Adverse events will be graded by a numerical score according to the defined NCI Common Terminology Criteria for Adverse Events (NCI CTCAE) and version number specified in the protocol. Adverse events not specifically defined in the NCI CTCAE will be scored on the Adverse Event log according to the general guidelines provided by the NCI CTCAE and as outlined below.

- Grade 1: Mild
- Grade 2: Moderate
- Grade 3: Severe or medically significant but not immediately life threatening
- Grade 4: Life threatening consequences
- Grade 5: Death related to the adverse event

Serious Adverse Events

OHRP and UTSW HRPP define serious adverse events as those events, occurring at any dose, which meets any of the following criteria:

- results in death;
- is life-threatening (places the subject at immediate risk of death from the event as it occurred);

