10.3 Data Analyses Plans

10.3.1 Primary endpoint: 2-year cumulative risk of local failure (i.e. anywhere in the larynx) following SBRT treatment of early glottic larynx cancer

This endpoint will be calculated using cumulative incidence statistics, with death as a competing risk.

10.3.2 Secondary endpoints:

Patient-reported outcomes: Difference in PRO voice quality measures between baseline and 1, 3, 6, 12, 18, 24, and 36 months following treatment:

10.3.2.1	VHI voice-quality score
10.3.2.2	EORTC QLQ-C30
	 Global health status
	 Physical functioning scale
	Role functioning scale
	Emotional functioning scale
	Cognitive functioning scale
	 Social functioning scale
10.3.2.3	EORTC HN35
	Speech
	 Social eating
	— • • • •

Social contact

These patient reported outcomes are single numeric scores that are collected at baseline, 1, 3, 6, 12, 18, 24 and 36 months from treatment. Patients with disease recurrence will be excluded. The changes in these outcomes from baseline to these timepoints will be analyzed using generalized estimated equations (GEE).

10.3.2.4 Rate of grade 3-5 acute (start of treatment through 90 days from the completion of treatment) and late (after 90 days from the completion of treatment) adverse events, according to NCI's CTCAE v4.0 toxicity criteria.

Only adverse events assessed to be definitely, probably, or possibly related to protocol treatment will be considered. The rates of all Grade 3-5 adverse events, and death during or within 30 days of discontinuation of protocol treatment will be characterized. Predictors of high-grade acute and late toxicity will be determined using multivariable logistic regression.

10.3.2.5Average patient utilities (derived from EQ-5D) at baseline, 3, 6,
12, 18, 24 and 36 months from the end of treatment

The average patient utilities (derived from EQ-5D) at baseline, 3, 6, 12, 18, 24 and 36 months from the end of treatment will be described. Changes in patient utility will be analyzed using generalized estimated equations (GEE). These models will be used to estimate the beta coefficient for dysphonia and grade 2-3 dysphagia, to produce an estimate of the utility decrement from this toxicity.

10.3.2.6 Cumulative risk of marginal and out-of-field local failure at 2 years from the start of treatment with death and prior in-field local failure as a competing risk

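### The late grade 3-5 endpoint has no organ limit, but the supplementary late record review covers three specialties and head-and-neck or gastrointestinal encounters only, so other severe events depend on direct reports and visits

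*Combined protocol and SAP*

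**What the plan says.** The endpoint appears in 2.4.2.2 and again in 10.1.2.2 as the rate of grade 3-5 acute and "late (after 90 days from the completion of treatment) adverse events", graded by CTCAE v4.0. Neither place names an organ system or an attribution limit.

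The analysis text in 10.3.2.4 adds a filter: "Only adverse events assessed to be definitely, probably, or possibly related to protocol treatment will be considered". Its next sentence reads "The rates of all Grade 3-5 adverse events, and death during or within 30 days of discontinuation of protocol treatment will be characterized".

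Section 7.2.1 fixes the late window: "Adverse effects occurring in the time period from the end of acute monitoring, to 36 months post treatment, will be defined as late adverse events". It then gives two sources of late events. The first is anything reported directly to a member of the study team, of any type. The second supplements it: "the study team will review encounters in the following select specialty categories relevant to study endpoints: radiation oncology, medical oncology, and otolaryngology". This second source is limited again by subject matter, to "encounters that related to any head and neck or gastrointestinal event or problem".

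Sections 4.6, 5.3 and 5.4 schedule follow-up visits to 36 months, with an interim history and a toxicity evaluation. After the first year these visits are at least every 6 months.

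**The concern.** The record review is the only active search for late events that does not depend on the patient attending and telling someone. It is narrower than the endpoint it serves. No text directs anyone to emergency department, inpatient, neurology, vascular or pulmonary records, although severe events may well be treated there.

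The protocol itself gives a reason to care about one such event. Section 1.1 refers to late ischemic risk after head and neck irradiation, and summary point 3 of section 1.4 says: "A reduced dose to nearby structures might improve toxicities, such as esophagitis and stroke from carotid atherosclerosis". A stroke would normally be managed outside the three listed specialties. Aspiration pneumonia is a second example.

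Section 1.4 asks whether hypofractionated treatment can be given with acceptable late toxicity and expects late toxicity to improve. The late grade 3-5 rate is the main figure bearing on that. If events are missed, the answer looks better than it should, and the regression for predictors of high-grade late toxicity planned in 10.3.2.4 loses events as well.

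**Working it through.** The plan gives no figure for detection or for the expected late event rate, so there is nothing of its own to reproduce. The check is a comparison of texts, followed by the arithmetic that N = 25 allows.

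**Scope of the endpoint against scope of each capture route**

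| Item | Source | Scope |
|---|---|---|
| Endpoint | 2.4.2.2, 10.1.2.2 | Grade 3-5, any organ system |
| Endpoint as analysed | 10.3.2.4 | At least possibly related to treatment |
| Direct report | 7.2.1 | Any type, if someone tells the team |
| Scheduled visits | 4.6, 5.3, 5.4 | Any type, if the patient attends and it is elicited; late visits at 6, 9, 12, 18, 24, 30 and 36 months |
| Record review | 7.2.1 | Three specialties, and head-and-neck or gastrointestinal encounters only |
| SAE reporting | 7.3.1 | Any type, from the time the team becomes aware |

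Reading down the table:

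1. Direct report and visits match the endpoint in scope, but both need an informant.
2. SAE reporting is a duty that starts with awareness. It does not detect events.
3. The relatedness filter removes unrelated events but cannot restore an unknown one. An event has to be found before it can be attributed.
4. The record review is the backstop when there is no informant, and it is the one late route with limits on specialty and event type.
5. Section 4.7 removes patients who cannot complete follow-up procedures because of cognitive impairment and returns them to standard-of-care follow-up. A stroke that impaired cognition could thus end study visits for the patient whose event should count.

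**Direction.** Section 4.2 makes every treated patient evaluable for toxicity, so a missed event leaves the numerator and not the denominator. The bias can only be downward.

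**Size per patient.** 1/25 = 0.04, or 4 percentage points.

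**Sensitivity to assumed inputs.** Let t be the true rate of possibly related late grade 3-5 events managed outside the reviewed encounters, and s the proportion of them that become known. Neither is in the documents. The expected observed rate is t × s, and the chance of seeing none in 25 patients is (1 − t × s)^25.

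| Assumed t | s | t × s | Chance of none in 25 |
|---|---|---|---|
| 8% | 100% | 8% | 12% |
| 8% | 75% | 6% | 21% |
| 8% | 50% | 4% | 36% |
| 8% | 25% | 2% | 60% |
| 4% | 100% | 4% | 36% |
| 4% | 50% | 2% | 60% |

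**Against sampling error.** The exact two-sided 95% interval is 2.5% to 31.2% for 3/25 and 1.0% to 26.0% for 2/25. With none observed, the upper limit is 13.7%.

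**The case against.** The record review is a supplement. Section 7.2.1 puts direct reports of any type first, and seven visits with toxicity evaluation fall in the late window. Hospitalization and death are SAEs that go to the monitoring committee within 5 business days of awareness, overall survival is an endpoint, and section 5.5.9 requires documented contact attempts over two years before a patient is considered lost. The endpoint is descriptive and no stopping rule depends on it. Missing one event of three moves the exact interval by less than its own width. All of this stands, and it limits the point to a gap in the backstop.

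Some stronger readings are tempting, and the documents do not support them:

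- **That the review could not find a stroke.** The subject-matter limit in 7.2.1 applies to encounters. A radiation oncology or otolaryngology note for larynx cancer is a head-and-neck encounter, and its interim history may record a stroke or an admission. Laryngeal airway problems are likewise head-and-neck problems on an ordinary reading.
- **That every late grade 3-5 event counts, related or not.** The second sentence quoted from 10.3.2.4 might suggest it, but the sentence before it restricts the analysis to events at least possibly related. Unrelated strokes or pneumonias would not enter the rate.
- **That this gap is what prevents a conclusion on stroke.** No stroke analysis is planned, and a single-arm study of 25 patients followed for 36 months could support little on stroke however wide the search.

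What the objection does not answer is the patient who dies, becomes disabled or stops attending. Awareness-based rules and visits give least there, and the record review is narrowest for care given in hospital.

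**Conclusion.** The point holds as a mismatch of scope. The endpoint is open to any organ system, while the active late record search is confined to three specialties and two problem areas. Possibly related severe events treated elsewhere rest on direct reports and on visits up to about 6 months apart after year 1.

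Any bias in the late rate is downward. A reader might want a percentage understatement, but the documents give neither the true rate nor the share of events that would go unreported, so none can be derived. What can be said is that each missed patient is 4 percentage points at N = 25; the table of detection rates is illustration on assumed inputs. One missed event is small against the sampling error of a study this size, but it is systematic in direction and can be prevented.

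This is a worthwhile low-cost improvement. It does not invalidate the toxicity endpoint.

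**What to change.** In the late adverse event paragraph of 7.2.1:

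- extend the encounter review to all emergency department and inpatient encounters, and to neurology/vascular and pulmonary encounters;
- add cerebrovascular and respiratory events to the event categories searched;
- keep the relatedness filter of 10.3.2.4.

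Leave 2.4.2.2 and 10.1.2.2 as they are. Narrowing the endpoint to head-and-neck and gastrointestinal events would make it match the present search, but it would discard related events of other types that direct reports and visits do capture.

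The cost is one amended paragraph and a wider record query for 25 patients: modestly more chart review, and more unrelated events for the team to attribute and set aside.

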3.0 SUBJECT ELIGIBILITY

Eligibility waivers are not permitted. Subjects must meet all of the inclusion and exclusion criteria to be registered to the study. Study treatment may not begin until a subject is registered.

3.1 Inclusion Criteria

- 3.1.1 Pathologically-proven diagnosis of squamous cell carcinoma *in situ*, squamous cell carcinoma or squamous cell variants (sarcomatoid, verrucous, basaloid, and papillary subtypes) involving the glottic larynx.
- 3.1.2 Clinical stage I-II (AJCC, 7th edition) with direct laryngoscopy showing no evidence of greater than stage II true glottic larynx cancer and PET/CT or CT neck showing no evidence of regional disease.
- 3.1.3 Age \geq 18 years.
- 3.1.4 ECOG Performance Status 0-2
- 3.1.5 Women of child-bearing potential and men must agree to use adequate contraception (hormonal or barrier method of birth control; abstinence) prior to study entry, for the duration of study participation, and for *90* days following completion of therapy. Should a woman become pregnant or suspect she is pregnant while participating in this study, she should inform her treating physician immediately.
 - 3.1.5.1 A female of child-bearing potential is any woman (regardless of sexual orientation, marital status, having undergone a tubal ligation, or remaining celibate by choice) who meets the following criteria:
 - Has not undergone a hysterectomy or bilateral oophorectomy; or
 - Has not been naturally postmenopausal for at least 12 consecutive months (i.e., has had menses at any time in the preceding 12 consecutive months).
- 3.1.6 Negative serum or urine pregnancy test within 2 weeks before registration for women of childbearing potential.
- 3.1.7 Ability to understand and the willingness to sign a written informed consent.
- 3.1.8 Patients with cognitive impairment or other limited decision making capacity with the ability to understand and willingly sign written informed consent or have the consent signed by a designated legally authorized representative (LAR).

3.2 Exclusion Criteria

- 3.2.1 AJCC stage III or stage IV larynx cancer
- 3.2.2 Involvement of the arytenoid cartilage beyond the vocal process.
- 3.2.3 Prior chemotherapy for treatment of the targeted larynx lesion.
- 3.2.4 Synchronous primaries in the head and neck
- 3.2.5 Prior radiotherapy to the region of the study cancer that would result in overlap of radiation fields.
- 3.2.6 Subjects smoking in excess of 1 pack of cigarettes per day.
- 3.2.7 Subjects may not be receiving any other investigational agents.

- 3.2.8 Uncontrolled intercurrent illness including, but not limited to, ongoing or active infection, symptomatic congestive heart failure, unstable angina pectoris, cardiac arrhythmia, or psychiatric illness/social situations that, in the opinion of the investigator, would limit compliance with study requirements.
- 3.2.9 Subjects must not be pregnant or nursing due to the potential for congenital abnormalities and the potential of this regimen to harm nursing infants.

4.0 TREATMENT PLAN

4.1 Treatment Dosage and Administration

Radiation will be delivered twice per week for 5 fractions (42.5 Gy cohort, low-risk) or daily for 16 fractions (58.08 Gy cohort, moderate-risk).

Low-risk is defined by:

- PTV less than 10 cc, AND
- No reported smoking within 1 month from registration

Moderate-risk is defined by:

- PTV greater than or equal to 10 cc, OR
- Smoking within 1 month from registration (no more than 1 pack per day)

4.1.1 Radiation Therapy

4.1.1.1 CT simulation

Patients will be simulated in a thermoplastic mask extending from the scalp through upper chest (e.g. "5 point mask"), using 1 mm thick slices. For SBRT planning, a CT simulation with IV contrast and a 4-D respiratory CT-scan focusing on the larynx are recommended but not required.

For Cyberknife patients treated with skin tracking, four gold fiducials will be placed on the skin, two on each side of the neck and at different vertical alignments in the vicinity of the larynx. Small tattoos will be placed at the site of each skin fiducial in order to replicate the fiducial placement for treatment.

For VMAT patients, the isocenter will be placed on the mask.

4.1.1.2 Primary tumor delineation and targeting

GTV: The gross tumor volume (GTV) will be contoured based on laryngoscopic findings by the investigator. Additional anatomic tumor location information obtained from biopsy procedure can be used to help guide GTV volumes. GTV volumes should be confirmed in both the sagittal and coronal views to verify that the involved areas of the vocal cord are covered. ITV: From the 4DCT at the time of simulation, the MIP, average, maximum inhalation and maximum exhalation scans from the 4D CT scan will be imported. The ITV should include the GTV plus any motion seen on the 4DCT scans.

CTV: this trial will not include a CTV volume.

PTV: The planning target volume (PTV) will include the ITV plus a 3 mm left-right and anterior-posterior expansion and a 5 mm cranio-caudal expansion.

4.1.1.3 Dose prescription

Patients treated on the 5 fraction regimen will be irradiated two times per week, with at least 2 days between fractions (i.e. Monday-Wednesday). Attempts should be made to start treatment on a Wedneday and end treatment on a Monday, to minimize the total treatment time.

Patients treated on the 16 fraction regimen will be irradiated once per day, every day.

4.1.1.4 Treatment planning

Patients will be treated using either CyberKnife or VMAT. Voxel doses will be calculated using the smallest voxel resolution available (i.e. 1.5 for VMAT plans in Eclipse and 1.25 for Cyberknife).

4.1.1.5 Coverage constraints

All plans must be normalized such that 95% of the volume of each PTV is covered by the prescription dose.

At a volume of 0.03 cc within each PTV volume, the dose should not exceed 115% of the prescription anywhere in the plan.

The arytenoid should not receive more than 102% or 105% of the prescription for the 5 and 16 fraction regimens, respectively.

